### **2. Good Clinical Practice Guidelines**

ICH GCP guidelines can be found at the following URLs:

[http://www.ich.org/fileadmin/Public\\_Web\\_Site/ICH\\_Products/Guidelines/Efficacy/E6/E6\\_R1\\_Guideline.pdf](http://www.ich.org/fileadmin/Public_Web_Site/ICH_Products/Guidelines/Efficacy/E6/E6_R1_Guideline.pdf)

[http://www.ich.org/fileadmin/Public\\_Web\\_Site/ICH\\_Products/Guidelines/Efficacy/E6/E6\\_R2\\_Step\\_4.pdf](http://www.ich.org/fileadmin/Public_Web_Site/ICH_Products/Guidelines/Efficacy/E6/E6_R2_Step_4.pdf)

| 9.6. | Physical Examination..... | 29 |
| 9.7. | Concomitant Medication..... | 29 |
| 10. | Changes from Planned Analysis | 29 |
| 11. | Other Planned Analysis..... | 30 |
| 11.1. | Pharmacokinetic Analysis..... | 30 |
| 12. | References..... | 30 |

List of Abbreviations

| ABBREVIATION | EXPLANATION |
|------------------|---|
| AE | adverse event |
| ANCOVA | analysis of covariance model |
| AUC | area-under-the-curve |
| BID | twice daily |
| CI | confidence interval |
| C _{max} | maximum concentration |
| COVID-19 | coronavirus disease 2019 |
| CRF | case report form |
| DSMB | data safety monitoring board |
| ECG | electrocardiogram |
| ECMO | extracorporeal membrane oxygenation |
| eCRF | electronic case report form |
| FDA | Food and Drug Administration |
| GCP | Good Clinical Practice |
| HFNC | high-flow nasal cannula |
| ICH | International Council for Harmonisation of Technical Requirements for Pharmaceuticals for Human Use |
| ICU | intensive care unit |
| IND | investigational new drug |
| INR | international normalized ratio |
| IP | investigational product |
| IRB | institutional review board |
| ITT | intent-to-treat |
| PD | pharmacodynamic |

| ABBREVIATION | EXPLANATION |
|---------------------|---|
| PK | pharmacokinetic |
| PP | per protocol |
| QD | once daily |
| SAE | serious adverse event |
| SAP | statistical analysis plan |
| SARS-CoV-2 | severe acute respiratory syndrome coronavirus 2 |
| sPLA2 | secretory phospholipase 2 |
| SpO ₂ | peripheral oxygen saturation |
| TEAE | treatment-emergent adverse event |
| TID | three times daily |
| T _{max} | time of maximum concentration |
| WHO | World Health Organization |

1. Overview

This statistical analysis plan (SAP) describes the planned analysis and reporting for Ophirex, Inc. protocol number OPX-PR-02 (A Phase 2, Randomized, Double-blind, Placebo-controlled Study to Evaluate the Safety, Tolerability, and Efficacy of Varespladib in Patients Hospitalized with Severe COVID 19 Caused by SARS-CoV-2 (STAIRS: Small molecule Targeting Acute Inflammatory and Respiratory Symptoms in SARS-CoV-2)), Version 3.0, dated 28-Feb-2022. Reference materials for this statistical plan include the protocol and the accompanying sample data collection documents. Operational aspects related to collection and timing of planned clinical assessments are not repeated in this SAP unless relevant to the planned analysis.

The structure and content of this SAP provides sufficient detail to meet the requirements identified by the Food and Drug Administration (FDA), European Medicines Agency (EMA), and International Conference on Harmonization (ICH) of Technical Requirements for Registration of Pharmaceuticals for Human Use: Guidance on Statistical Principles in Clinical Trials (ICH, 1998). All work planned and reported for this SAP will follow internationally accepted guidelines, published by the American Statistical Association (ASA, 2018) and the Royal Statistical Society (RSS, 2014), for statistical practice.

The planned analyses identified in this SAP may be included in clinical study reports (CSRs), regulatory submissions, or future manuscripts. Also, post-hoc exploratory analyses not necessarily identified in this SAP may be performed to further examine study data. Any post-hoc or unplanned, exploratory analysis performed will be clearly identified as such in the final CSR.

The statistical plan described hereafter is an *a priori* plan. It will be approved before any unblinded inferential or descriptive analysis of data pertaining to Ophirex, Inc.'s study OPX-PR-02.

2. Study Objectives and Endpoints

2.1. Study Objectives

2.1.1. Primary Objective

The primary objective is to evaluate the safety, tolerability, and efficacy of varespladib in patients hospitalized with severe COVID-19 when given in addition to the institutional standard of care.

2.1.2. Secondary Objectives

The secondary objectives are:

- To evaluate the efficacy of varespladib in reducing the need for respiratory support
- To evaluate the efficacy of varespladib in reducing the duration of hospitalization
- To evaluate the efficacy of varespladib in improving time to recovery

- To evaluate time to resolution of symptoms
- To evaluate the efficacy of varespladib in reducing the incidence of morbidity and mortality.

2.1.3. Exploratory Objectives

The exploratory objectives are:

- To assess the pharmacokinetics of varespladib in COVID-19 patients
- To evaluate the overall effect of varespladib in suppression of sPLA2 with severe acute respiratory syndrome coronavirus 2 (SARS-CoV-2) infection
- To assess pharmacoeconomic endpoints

2.2. Study Endpoints

2.2.1. Efficacy Endpoints

2.2.1.1. Primary Efficacy Endpoint

The primary efficacy endpoint of this study is a proportion of participants alive and free of respiratory failure at Day 28.

The primary estimand for the primary efficacy endpoint of this study is a proportion of participants alive and free of respiratory failure at Day 28.

2.2.1.2. Secondary Efficacy Endpoint(s)

The secondary efficacy endpoints of this study include the following:

- Clinical improvement as measured by the World Health Organization (WHO) 9-point ordinal scale from baseline through Day 60
- Time to and proportion of participants with all-cause mortality through Day 60
- Proportion of participants who experienced respiratory failure within the first 28 days after randomization
- Among patients that never experience respiratory failure in the first 28 days, time to initiation, duration, and proportion of subjects receiving supplemental oxygen or other respiratory support within the first 28 days after randomization
- Among patients that experience respiratory failure in the first 28 days, time to initiation and duration of the forms of respiratory support meeting criteria outlined in critical COVID criteria (exclusion criteria 1.c.i) within the first 28 days after randomization
- Number of days of oxygen support through Day 28 after randomization
- SpO₂ through Day 28 after randomization

- Number of ventilator-free days through Day 28 after randomization
- Number of hospitalization days through Day 28 after randomization
- Number of days without renal stabilization and/or replacement through Day 28 after randomization
- Number of organ failure-free days through Day 28 after randomization
- Number of days at elevated level of care (ICU) through Day 28 after randomization
- Number of healthcare encounters through Day 28 after randomization

2.2.1.3. Exploratory Efficacy Endpoint(s)

The exploratory efficacy endpoints of this study include the following:

- sPLA2 within blood samples from baseline through Day 28 after randomization

2.2.2. Safety Endpoints

The safety endpoints of this study include the following:

- Incidence and severity (based on National Cancer Institute [NCI] Common Terminology Criteria for Adverse Events [CTCAE] v5.0 grade) of AEs, SAEs, and AEs leading to discontinuation of IP
- Vital signs
- Changes in levels of biomarkers: cardiac troponin, C-reactive protein (CRP), and ferritin
- Clinical laboratory evaluations
- 12-lead electrocardiograms (ECGs)

2.2.3. Pharmacokinetic Variables (Exploratory)

The PK endpoints for the study include PK parameters for varespladib:

- PK Parameters

2.2.4. Pharmacokinetic Variables (Exploratory)

- Selected secondary endpoints, to include number of healthcare encounters, number of hospitalization days, and number of days at elevated level of care (ICU), all through Day 28

3. Overall Study Design and Plan

3.1. Overall Design

This is a 2-part, multi-center, randomized, double-blind, placebo-controlled, phase 2 study designed to evaluate the safety, tolerability, and efficacy of oral varespladib, in addition to standard of care, in patients hospitalized with severe COVID-19 caused by SARS-CoV-2.

Approximately 90 participants will be randomized, 18 in Part 1 and 72 in Part 2. Participants must be 18 to 80 years of age and have severe laboratory-confirmed COVID-19.

The study will be conducted in 2 parts. Both parts will be randomized and double-blind. Part 1 will be dose-finding in 4 parallel treatment groups randomized to treatment with varespladib (at 250 mg once daily [QD], twice daily [BID], or three times daily [TID] [total doses of 250, 500, or 750 mg/day]) or placebo in a 5:5:5:3 ratio. After all participants in Part 1 have completed Day 28, a data safety monitoring board (DSMB) will review the safety results from Part 1 and will recommend the dose regimen to be used in Part 2. Part 2 will randomize an additional 72 participants to the dose regimen selected from Part 1 or placebo in a 1:1 ratio.

In both parts of the study, eligible participants will be enrolled and randomized to receive either varespladib or placebo in addition to institutional standard of care for 7 days.

3.2. Sample Size and Power

Approximately 90 evaluable participants are planned for this study. Eighteen participants will be randomized into Part 1 of the study in a 5:5:5:3 ratio with 3 varespladib arms and a placebo arm. In Part 2 of the study, 72 participants will be randomized in a 1:1 ratio with the selected varespladib arm from Part 1 of the study and a placebo arm. No stratification variables will be used.

This is a pilot study and exploratory in nature. The sample size is not based on a formal power calculation.

3.3. Study Population

Participants will be adults aged 18 to 80 years diagnosed with severe laboratory-confirmed COVID-19 requiring hospitalization caused by severe acute respiratory syndrome coronavirus 2 (SARS-CoV-2).

3.4. Treatments Administered

Varespladib or placebo will be administered in addition to institutional standard of care. The written institutional standard of care at each site may change during the study.

3.5. Method of Assigning Participants to Treatment Groups

In Part 1, varespladib or placebo will be administered in addition to institutional standard of care for 7 days at a dosage of 250 mg QD, BID, or TID (total doses of 250, 500, or 750 mg/day).

Table 1: Treatment groups in Part 1

| Randomized Treatment | Morning | Afternoon | Bedtime |
|----------------------|---------|-----------|---------|
| 250 mg QD | 250 mg | placebo | placebo |
| 250 mg BID | 250 mg | placebo | 250 mg |
| 250 mg TID | 250 mg | 250 mg | 250 mg |
| placebo | placebo | placebo | placebo |

Any dose that is missed should not be taken later that day.

In Part 2, varespladib or placebo will be administered in addition to institutional standard of care for 7 days using the dose regimen selected from Part 1.

3.6. Blinding and Unblinding

All participants, investigators, and study personnel involved in the conduct of the study, including data management, will be blinded to treatment assignment with the exception of a specified unblinded statistician and programmer who will have access to the randomization code, and the DSMB. In Part 1 only, secondary pharmacists, separate from other study staff, will be unblinded to ensure the correct cartons are assigned to morning, noon, and evening. Unblinded pharmacists will have no other study participation or activities.

Unblinding will be permitted in a medical emergency that requires immediate knowledge of the subject's treatment assignment. If a subject's treatment assignment is unblinded, he/she may or may not be asked to withdraw from the study. The investigator will make this decision after consultation with the medical monitor.

3.7. Schedule of Events

Please see the protocol Table 2-1 for a detailed schedule of events.

4. Statistical Analysis and Reporting

4.1. Introduction

Data processing, tabulation of descriptive statistics, calculation of inferential statistics, and graphical representations except for PK parameter estimation will primarily use SAS (release 9.3 or later). All PK parameter estimations will use WinNonlin® version 6.4 or later. If the use of other software is warranted, the final CSR will detail what software was used for what purposes.

Continuous (quantitative) variable summaries will include the number of participants (n) with non-missing values, mean, standard deviation (SD), median, minimum, and maximum.

Categorical (qualitative) variable summaries will include the frequency and percentage of participants who are in the particular category for each possible value. In general, the denominator for the percentage calculation will be based upon the total number of participants in the study population for the treatment groups, unless otherwise specified.

The minimum and maximum will be reported with the same degree of precision (ie, the same number of decimal places) as the observed data. Measures of location (mean and median) will be reported to 1 degree of precision more than the observed data and measures of spread (SD) will be reported to 2 degrees of precision more than the observed data.

Percentages will be presented to 1 decimal place, unless otherwise specified.

Unless otherwise indicated, comparative statistics between treatment and control group will report point estimates, p-values, and 95% confidence intervals with the goal of understanding the clinical importance of observed effects.

This study is considered an exploratory study. Statistical tests will be interpreted in an exploratory sense only and will not be considered formal hypothesis tests.

4.2. Interim Analysis and Data Monitoring

No interim analyses are planned.

An independent Data Safety Monitoring Board (DSMB) will operate under a charter that will be finalized prior to the start of the study. After all participants in Part 1 have completed Day 28, the DSMB will review results from Part 1, including all available safety data through Day 60, and will recommend the dose regimen to be used in Part 2. During Part 2, the DSMB will evaluate unblinded data, including data by group, at the intervals specified in the DSMB charter. In case of significant toxicity, the DSMB may choose to review the available safety data and recommend pausing or stopping recruitment in a particular dose group or the study as a whole. Efforts will be made to collect all follow-up and safety data through Day 60 for all patients enrolled in the study.

5. Analysis Populations

The following 5 analysis populations are planned for this study:

- **Intent-to-treat Population (ITT):** All randomized participants.
- **Safety Population (SAF):** All participants who receive at least 1 dose of IP.
- **Per-protocol Population (PP):** All randomized participants with at least 1 dose of IP with no key protocol deviations during the study that would affect the interpretation of the primary efficacy assessments. Inclusion in the PP population will be determined prior to database lock and unblinding of treatment assignment.

- **Pharmacokinetic Population (PK):** All randomized participants who receive at least 1 dose of IP and provide at least 1 evaluable post-dose PK measurement.
- **Combined Population:** All participants who receive at least 1 dose of placebo or at least 1 dose of IP at the dose regimen used in Part 2.

Assignment of participants to populations will be determined prior to the study database lock.

The Safety Population will be used to analyze the safety endpoints, the ITT Population will be used to analyze the efficacy endpoints, and the PK population will be used to analyze the PK endpoints. In addition to the ITT Population, the PP and Combined Populations will be used to analyze the primary efficacy endpoint. Secondary endpoints will also be analyzed using the Combined Population.

Part 1 efficacy data will be listed. Part 1 participants receiving placebo or the dose regimen used in Part 2 will be included in the Combined Population. Safety and PK analyses will be based on actual treatment received. For the efficacy analyses, in the event that a subject is randomized incorrectly or is given the incorrect IP, analyses of the ITT, PP, and Combined Populations will be based on the randomized treatment.

6. General Issues for Statistical Analysis

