## 9. TREATMENTS

### 9.1. Identification of Investigational Products

The investigational products (IPs) in this study are varespladib and matching placebo.

- Varespladib-methyl (LY333013)
  - 250 mg immediate-release oblong, white, film-coated tablet for oral administration
- Placebo
  - Oral formulation matched to the oral varespladib tablet

LY333013 contains the excipients anhydrous lactose United States pharmacopeia (USP)/National Formulary (NF), lactose monohydrate USP/NF, hydroxypropyl cellulose USP/NF, polysorbate 80 (vegetable source) USP/NF, microcrystalline cellulose USP/NF, croscarmellose sodium USP/NF, magnesium stearate (vegetable source) USP/NF, and the film coat Opadry II 85F18422 White.

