#### 13.1.1 Analysis Populations

The following 5 analysis populations are planned for this study:

- **Intent-to-treat (ITT):** All randomized participants.
- **Safety:** All participants who receive at least 1 dose of IP.
- **Per-protocol (PP):** All randomized participants with at least 1 dose of IP with no key protocol deviations during the study that would affect the interpretation of the primary efficacy assessments. Inclusion in the PP population will be determined prior to database lock and unblinding of treatment assignment.
- **Pharmacokinetic (PK):** All randomized participants who receive at least 1 dose of IP and provide at least 1 evaluable post-dose PK measurement.

- **Combined Population:** All participants in Part 2 and all participants in Part 1 assigned to the dose regimen selected for Part 2, who receive at least 1 dose of IP at the dose regimen used in Part 2.

Assignment of participants to populations will be determined prior to database lock.

The Safety Population will be used to analyze the safety endpoints, the ITT Population will be used to analyze the efficacy endpoints, and the PK population will be used to analyze the PK endpoints. In addition to the ITT Population, the PP and Combined Populations will be used to analyze the primary efficacy endpoint.

Part 1 efficacy data will be listed. Part 1 participants receiving placebo or the dose regimen used in Part 2 will be included in the Combined Population. Safety and PK analyses will be based on actual treatment received. For the efficacy analyses, in the event that a participant is randomized incorrectly or is given the incorrect IP, analyses of the ITT, PP, and Combined populations will be based on the randomized treatment.

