8.1. Primary Efficacy Analysis

The primary efficacy endpoint is the proportion of participants alive and free of respiratory failure at Day 28.

The proportion of respiratory failure-free surviving participants in each Part 2 treatment group at Day 28 will be analyzed using logistic regression with treatment as a factor and age, diabetes, body mass index, and baseline sPLA2 activity included as covariates. Dummy/reference coding will be used in all logistic regression implementations. The risk difference between varespladib and placebo along with the 95% CI and p-value will be presented. Note that logistic regression typically involves calculation and testing of odds ratios, however, this analysis will focus on presenting and testing the risk difference via the delta method ([Ge et al, 2011](#)).

The ITT, PP and Combined populations will be used to analyze the primary efficacy endpoint. The ITT population will be the primary population for the efficacy analyses.

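### The Combined Population bullets differ between protocol and SAP and from the sentence both documents share, and the Combined models leave out study part; the effect is small and matters only if Part 2 resumes

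*SAP*

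**What the plan says.** **Membership.** Three statements define the set.

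- Protocol 13.1.1, bullet: "All participants in Part 2 and all participants in Part 1 assigned to the dose regimen selected for Part 2", with the condition "who receive at least 1 dose of IP at the dose regimen used in Part 2". Part 1 placebo is not named.
- SAP section 5, bullet: "All participants who receive at least 1 dose of placebo or at least 1 dose of IP", the IP dose being one at the Part 2 regimen.
- Protocol 13.1.1, closing paragraph, with the same sentence in SAP section 5: "Part 1 participants receiving placebo or the dose regimen used in Part 2 will be included in the Combined Population".

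Two definitions bear on how these read. Protocol 9.1 states: "The investigational products (IPs) in this study are varespladib and matching placebo". The SAP bullet, by contrast, sets placebo and IP side by side as alternatives. The Part 1 dosing tables (protocol 9.2, SAP 3.5) show that the active QD and BID arms take placebo tablets to keep the blind. The QD row of the SAP table reads "250 mg QD | 250 mg | placebo | placebo".

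**Use.** SAP 8.1 says: "The ITT, PP and Combined populations will be used to analyze the primary efficacy endpoint". SAP section 5 and 8.2 extend the Combined Population to the secondary endpoints. ITT is the primary population.

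**Model.** SAP 6.1.2 applies covariate adjustment to the Combined Population and lists diabetes, age, body mass index and baseline sPLA2 activity. Others may be considered if the arms are significantly imbalanced. Neither that section nor SAP 8.1 has a term or stratum for study part.

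**Current status.** SAP section 10 records a recruitment pause with 18 participants in Part 1 and one in Part 2. Efficacy reporting now uses the Part 1 ITT population without hypothesis tests. A protocol and SAP amendment is foreseen for Part 2, for two of the secondary endpoints.

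**The concern.** A population used for the primary endpoint and every secondary endpoint should have one definition that two programmers would code the same way. Here the bullets, each taken alone, give different sets. One leaves out concurrent controls. The other can admit doses that were not carried forward. Part 1 results are to be reported unblinded, so if Part 2 resumes under the present wording, membership would be settled when some of the outcomes are already known.

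The second issue is comparability. The two parts are separate randomisations with different allocation ratios, run one after the other. The documents give reasons why outcomes could differ by part: enrolment periods of about six months each (protocol 10.1), institutional standard of care that may change during the study (protocol 9.9, SAP 3.4), and different handling of missed doses (protocol 9.2). When allocation differs by part and part is left out of the model, a share of any between-part difference in outcome is counted as treatment effect.

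**Working it through.** **Inputs.** Part 1: 18 participants at 5:5:5:3. Part 2: 72 at 1:1 (both SAP 3.2). The plan's total reproduces: 5+5+5+3 = 18, and 18+72 = 90. The documents give no size for the Combined Population, no response rate and no power calculation. Response rates (60 to 90% alive and free of respiratory failure) and between-part gaps (5 to 30 points) are therefore assumptions.

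**Step 1: membership under each reading, at planned numbers.**

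| Reading | Varespladib v placebo | N |
|---|---|---|
| Shared sentence | 36+5 = 41 v 36+3 = 39 | 80 |
| Protocol bullet alone, IP including placebo (protocol 9.1) | 41 v 36 | 77 |
| Protocol bullet alone, IP meaning varespladib only | 41 v 0 | no comparator |
| SAP bullet literally, QD or BID selected | adds 5 from the other of these two arms | 85 |
| SAP bullet literally, TID selected | adds 10 from QD and BID | 90 |

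For the literal SAP reading, QD + BID + placebo in Part 1 is 5+5+3 = 13, and 72+13 = 85. If TID is selected, its 5 participants also enter, giving 90.

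**Step 2: imbalance of study part between arms (N=80).** Part 1 supplies 5/41 = 12.2% of varespladib and 3/39 = 7.7% of placebo. The difference is 4.5 points.

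**Step 3: bias of a risk difference with no part term.** Bias = (Part 1 share of active − Part 1 share of placebo) × between-part gap.

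| Assumed gap | 41 v 39 | 41 v 36 |
|---|---|---|
| 5 points | 0.2 | 0.6 |
| 10 points | 0.5 | 1.2 |
| 20 points | 0.9 | 2.4 |
| 30 points | 1.4 | 3.7 |

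For example, 0.045 × 20 = 0.9. In the right-hand column the share difference is 5/41 − 0/36 = 12.2 points.

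**Step 4: scale.** The 95% half-width is 1.96 × √[p(1−p)(1/41+1/39)]. It is 13.2 points at p = 0.9 and 21.5 points at p = 0.6.

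**Step 5: error rate.** A simulation had 400,000 replicates, no treatment effect, no covariates, a Part 2 rate of 75% and Part 1 rates of 45, 55, 75 and 95%. Type I error at nominal 5% was 4.9 to 5.1% pooled and about 4.9% with a Mantel-Haenszel test stratified by part. The mean pooled risk difference was −1.3, −0.9, 0.0 and +0.9 points. The stratified one was about zero throughout.

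**Step 6: cost of stratifying.** Effective-size weight pooled: 41×39/80 = 19.99. Stratified: 36×36/72 + 5×3/8 = 18 + 1.875 = 19.875. The loss is 0.1125/19.9875 = 0.6%.

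**Step 7: would the imbalance clause bring study part in?** For 5/41 v 3/39, Fisher's exact p = 0.71. A rule triggered by significant imbalance would not be expected to add it.

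**The case against.** The strongest reply is that the intended set can be recovered. The shared sentence stands in both documents, in the SAP shortly after the bullet, and gives 41 v 39. A reader might infer from the bullets that nobody can tell who is in the Combined Population, and the documents do not support that. Placebo is also a named randomised arm in the Part 1 tables, so counting a QD or BID participant through blinding tablets is a strained reading. Such a participant would have no natural place in a varespladib v placebo comparison. Both points stand. They do not remove the need to align the text: the shared sentence speaks of participants receiving placebo, which carries the same tablet-or-arm ambiguity. The rule that analyses follow randomised treatment is written for misrandomisation or wrong IP and does not settle membership.

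A reader might also infer that the two parts are pooled without adjustment. They are not: SAP 6.1.2 applies four covariates to the Combined analyses, and only study part is missing. Nor is there support for reading the 5:3 and 1:1 mix as a serious distortion. Under the N=80 reading, 4.5% of any between-part gap passes into the estimate, and type I error is essentially unchanged.

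Finally, the Combined analysis is supplementary to ITT, tests are declared exploratory, and under SAP section 10 it has no role in the current report. That stands and limits the weight of the point. It also means that dropping p-values from Combined results would be a reporting preference, not a correction.

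**Conclusion.** The point holds in a limited form. The two bullets differ from each other and from the sentence both documents carry, and the Combined models omit study part although the parts were planned as separate randomisations at different ratios. The definition is the weightier half: depending on the text followed, N is 77, 80, 85 or 90 at planned enrolment, with 80 the evident intent. The missing part term moves the risk difference by about 0.2 to 1.4 points under that intent, or 0.6 to 3.7 points if Part 1 placebo were left out. These figures rest on full planned enrolment and on assumed between-part gaps of 5 to 30 points, which have no source in the documents. The planned total of 90 and the ITT analysis are unaffected. The consequence arises only if Part 2 resumes.

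**What to change.** Make both changes in the protocol and SAP amendment that SAP section 10 already foresees.

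1. **One definition in both documents, by randomised arm.** Combined = all Part 2 participants, plus Part 1 participants randomised to the selected regimen or to the placebo arm, who took at least 1 dose of their assigned IP. Use IP in the sense of protocol 9.1, so that placebo is included. Delete or reword the shared sentence to match.
2. **Stratify Combined analyses by study part.** Use Mantel-Haenszel weights by part for risk differences, a part stratum in the Cox models, and a part term in the ANCOVA models. Do not rely on a part coefficient in the logistic model. It would rest on 8 Part 1 participants, and if the response rate is 80 to 90% (assumed), the chance that all 8 respond is 0.8^8 = 17% to 0.9^8 = 43%, in which case the coefficient cannot be estimated.

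The cost is a wording edit in two documents, a modest change to the Combined programs (the SAP must also say how the Mantel-Haenszel estimate sits beside the covariate-adjusted one), and about 0.6% of effective size. No data collection changes.
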